## 7.1.4 Exploratory Endpoints

Levels of specific markers involved in regulation of T cell activation and lymphocyte infiltration as assessed in the tumor immune microenvironment and the systemic immune response.

Protocol/Amendment No.: UVA-LACC-PD201, Version 4.0, 06 March 2018

## 7.2 Sample size and accrual

Results in Jordanova ES, et al 2008, report estimates of CD8+/Treg for normal cervix and cervical cancers tissue for cervical cancer patients who underwent radical hysterectomy with lymphadenectomy.[4] These data provide the assumed "natural baseline" of cancer patients' in this study with CD8+/Tregs being lower in cancer tissue, and results in a Cohen's *d*av effect size (ES) of 0.45. Estimated sample size is based upon being able to detect a similar effect size between CD8+/Tregs at baseline and end of CRT, and baseline to the 12 weeks post CRT assessment without correction for multiple comparisons. Data from Nilges, K et al, 2003, indicates a mean (standard deviation) of 23.32 (15.39) in CD8+/Tregs measured in the tumor infiltrating lymphocytes (TIL) from patients with cervical cancer. Given these data, 44 eligible patients are required (per arm) to assess change in pre/post CD8+/Tregs with an ES of 0.45 with type I and II errors of 10%. Each within arm comparison supports the following hypothesis. Cisplatin can kill T cells, therefore the CRT may eliminate both CD8+ HPV CTL and Tregs, and the ensuing or concurrent pembrolizumab treatment may increase the CD8+/Treg ratio (test that pembrolizumab will increase CD8+/Tregs to an ES of 0.45).

Adjusting for an overall 10% ineligibility/drop-out rate, maximum accrual to the study is estimated at 98 patients. Accrual is estimated at 4 patients a month, thus accrual to the study should be completed by 2.0 years with primary analysis at 3 years.

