## 7.0 STATISTICAL CONSIDERATIONS

This is a randomized phase II study to assess the safety of CRT in combination with pembrolizumab given as consolidation therapy or current with CRT, and to obtain preliminary estimates of the immunologic effect of the addition of pembrolizumab to CRT in this patient population. Eligible participants will be randomized 1:1 between the two arms. All participants receiving any protocol treatment will be evaluated for safety and the primary immunologic endpoint which is the ratio of the phenotype of HPV-specific CD8+ T cells to regulatory T cells (CD8+/Treg). Patterns of change in other immunologic endpoints assessed in the tissue and blood will be estimated along with 90% confidence intervals. The purpose is not to make definitive comparisons between arms but to obtain preliminary estimates of change in CD8+ T-cells and regulatory T cells over time for the different treatment schedules.

Arm 1: pembrolizumab after completion of CRT Arm 2: pembrolizumab concurrent to CRT

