#### 7.5 Analyses

The study is designed with sufficient power to assess pre/post change in immune measures with an ES of .45 within each arm and not to detect a predetermined difference in the changes overtime between the two arms. However, data from the study will be used to estimate; the magnitude of the difference in pre/post change for all parameters of interest between the two arms; as well as progression—free and overall survival. With 44 eligible patients per arm we have 67%, 75% and 87% power to detect an ES of 0.45, 0.5 and 0.6, respectively, for continuous immune parameters (normality assumed) with a 10% level t-test. With 44 patients the width of a 90% CI (exact Clopper-Pearson) around the complete metabolic response at 3 months of 70% and the distant metastases rate at 3 years of 20% are (57%, 81%) and (10%, 33%), respectively. Thus, any estimated rate outside of these bounds would be considered promising. For each arm, progression free survival (PFS) and overall survival will be estimated by the product-limit method of Kaplan and Meier along with 90% confidence bands. In patients with complete metabolic response at 3 months, 3-year PFS is 78% (Schwartz et al, 2007). This result will be used to guide interpretation of results on PFS from this study.

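### Does the 44 per arm in Section 7.2 depend on a pre/post correlation that the plan never states?

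*Combined protocol and SAP*

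**What the plan says.** Section 7.2 starts from a published comparison of the CD8+/Treg ratio in normal cervix and cervical cancer tissue, which it summarises as a Cohen's d_av. It then sets the target by analogy: "effect size (ES) of 0.45. Estimated sample size is based upon being able to detect a similar effect size". The contrasts are within arm. The aim is to "detect a similar effect size between CD8+/Tregs at baseline and end of CRT, and baseline to the 12 weeks post CRT assessment", with no multiplicity correction. The requirement follows: "44 eligible patients are required (per arm) to assess change in pre/post CD8+/Tregs with an ES of 0.45 with type I and II errors", each error being set at 10%. The effect size in that sentence has no subscript. The only SD given comes from one set of measurements; a second cited study "indicates a mean (standard deviation) of 23.32 (15.39) in CD8+/Tregs measured in the tumor infiltrating lymphocytes (TIL").

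The hypothesis at the end of that paragraph is directional ("test that pembrolizumab will increase CD8+/Tregs to an ES of 0.45"), and Section 7.2 does not say whether the test is one- or two-sided.

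Section 7.5 repeats the claim: "The study is designed with sufficient power to assess pre/post change in immune measures with an ES of .45 within each arm". It then adds that with 44 per arm "we have 67%, 75% and 87% power to detect an ES of 0.45, 0.5 and 0.6, respectively, for continuous immune parameters", using a 10% t-test under normality. Neither section gives a pre/post correlation or an SD of the change.

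**The concern.** A d_av and a standardised paired change are different quantities. The first divides the mean difference by the average of the two SDs. The second divides it by the SD of the within-patient differences, which depends on how strongly baseline and follow-up values correlate. If 0.45 is a d_av, a sample size for a paired comparison needs that correlation, and the plan does not supply it.

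The correlation cannot be taken for granted. Section 7.2 itself suggests that chemoradiation may remove both cell populations in the ratio, so post-treatment values might track baseline poorly. The 10% type II error is the stated reason for 44 per arm. If it holds only under an undeclared assumption, a null within-arm change could be reported as coming from a 90% powered comparison when the real power was lower.

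There is also an apparent clash. Section 7.2 claims 90% power at an effect size of 0.45, while Section 7.5 quotes 67% at the same value.

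**Working it through.** **Inputs from the documents.** Effect size 0.45; type I error 10%; type II error 10%; 44 eligible patients per arm; within-arm pre/post comparison (7.2). Normality and a 10% t-test (7.5). The correlation r is not given, so the values used below are an assumed range.

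**Step 1: reproduce the 44.** For a paired t-test on n differences, the noncentrality is d_z × √n with n − 1 degrees of freedom.

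- Normal approximation, two-sided 10%: ((1.645 + 1.282) / 0.45)² = 42.3, so 43.
- Exact noncentral t, two-sided 10%, d_z = 0.45: at n = 44 the noncentrality is 0.45 × √44 = 2.985 and power is 90.2%; at n = 43 power is 89.6%. The smallest n that reaches 90% is 44.
- Exact, one-sided 10%: 34 pairs would be enough, and 44 would give 95.3%.

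The plan's figure is therefore the two-sided paired calculation with 0.45 entered as the mean change in SDs of the change.

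**Step 2: check sidedness and the 67% in Section 7.5.** For a two-sample t-test with 44 per arm, the noncentrality is d × √22 with 86 degrees of freedom.

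| Effect size | Plan (7.5) | Two-sided 10% | One-sided 10% |
|---|---|---|---|
| 0.45 | 67% | 67.3% | 79.4% |
| 0.50 | 75% | 75.2% | 85.4% |
| 0.60 | 87% | 87.4% | 93.6% |

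The Section 7.5 powers are for the comparison between arms, two-sided. They do not conflict with the within-arm 90%. They also confirm the sidedness that Section 7.2 leaves unsaid.

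**Step 3: what follows if 0.45 is a d_av.** With equal SDs at the two times, the SD of the change is SD × √(2(1 − r)), so d_z = d_av / √(2(1 − r)). At r = 0.5 the divisor is 1 and the two measures coincide. For 44 pairs, two-sided 10%:

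| Assumed r | d_z | Power at n = 44 | n for 90% power |
|---|---|---|---|
| 0 | 0.318 | 66.7% | 86 |
| 0.3 | 0.380 | 79.9% | 61 |
| 0.5 | 0.450 | 90.2% | 44 |
| 0.7 | 0.581 | 98.4% | 27 |

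The break-even correlation is 0.496. It rises if the SDs differ. At an assumed SD ratio of 2 it is 0.68 if d_av uses the arithmetic mean of the SDs, and 0.62 if it uses the root mean square.

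**Step 4: what depends on the answer.** The futility rule in 7.4.2 counts patients with the potential to respond, and the safety rule in 7.4.1 counts dose-limiting toxicities. Neither uses this test. A within-arm t-test or interval takes its standard error from the observed differences, so no planning value of r enters it.

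**The case for a change.** The best case for a change is that Section 7.2 names one effect measure and then sizes the trial for a similar effect, so the natural chain is d_av throughout. On that chain the 10% type II error lacks an input. The plan's account of chemoradiation gives some reason to doubt a high correlation, and power at r = 0 would be about 67%. Section 7.0 disclaims definitive comparisons between arms only; for change within an arm, 7.2 speaks of a test and 7.5 of sufficient power. A line of text would settle the matter at no cost.

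Part of this stands. The text does not say which measure the second 0.45 is, and on the d_av reading the missing correlation matters to the power statement. It does not show a wrong figure, however. The d_av label belongs to the cited tissue comparison, while the sizing sentence and Section 7.5 attach the unlabelled 0.45 to pre/post change. The exact match at 44 supports a standardised change, although it cannot exclude a d_av with r = 0.5 assumed, which gives the same n. Nor does the d_av reading imply low power, since any r above about 0.5 puts power over 90%. Doubt about sidedness is removed by the plan's own numbers.

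**Conclusion.** No change is needed. This is a gap in labelling that analysts fill sensibly. Read as a mean change of 0.45 SDs of the change, with a two-sided 10% paired t-test, the plan's 44 per arm and 10% type II error are exactly right (90.2% power) and require no correlation. Read as a d_av with equal SDs, the same claim needs r of about 0.5; over an assumed range of r from 0 to 0.7, power would run from 67% to 98%, so the text does not establish a shortfall.

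Under either reading the trial enrols the same number, runs the same analyses and applies the same stopping rules. Section 7.0 describes the aim as preliminary estimation of change, and the precision of those estimates will come from the observed differences. What remains is a point of reporting: anyone who quotes the 90% should describe it as power for 0.45 SDs of the change.

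This conclusion assumes approximate normality and 44 evaluable pairs per arm. Whether 0.45 was a sound value to borrow from the cited tissue comparison cannot be judged from the documents.

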## 4.3 Rationale

## 4.3.1 Rationale for the Trial and Selected Subject Population

We hypothesize that CRT in LACC will be beneficial to the immunostimulatory activity of pembrolizumab compared to single agent use. This hypothesis is based on evidence that platinumbased DNA intercalators and irradiation are highly effective at inducing a form of apoptosis known as immunological cell death (ICD),[8] which can lead to auto-vaccination that is promoted by blocking checkpoint molecules such as PD-1. We anticipate that ICD will not only curtail the immunosuppressive activity of T cells, but will also increase the source of antigen and improve the context of antigen presentation (by activating dendritic cells) that could lead to greater immune cell activation in the cervical cancer environment. However, cisplatin is deleterious to activated effector T cells (our unpublished data), and irradiation and chemotherapy can recruit myeloid cells and regulatory cells with immunosuppressive function.[9, 10] Therefore, the sequencing of SOC with PD-1 blockade deserves considerable attention, with the intent of defining optimal treatment regimens and the development of prognostic and predictive biomarkers. These observations suggest that PD-1 blockade is a potential therapeutic strategy to increase immune responses against cervical cancer. Pembrolizumab (MK-3475) is an PD-1 antibody approved for use in melanoma,[11] and the proposed study focuses on evaluating the influence of the addition of pembrolizumab to standard CRT, and sequencing of pembrolizumab with CRT, on CD8+ infiltrating T cells in subjects with locally advanced cervical cancer.

Secondary objectives of the study will estimate clinical endpoints to obtain preliminary data regarding the potential clinical effect of the combination. We will estimate the rate of complete metabolic response as measured by PET/CT at 12 weeks, as well as the rate of distant (versus local) recurrence.

There is no data available to predict the optimal time point to incorporate immunotherapy into a treatment course. Therefore, this study will evaluate biological endpoints and responses to immunotherapy given at the time of chemotherapy and following completion of chemotherapy.

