These studies will provide a direct assessment of the capability of PD-1 blockade to augment T cell responses initiated by CRT-induced ICD and DC activation. Our current trial design will allow us to detect acute effects of these study drugs on the immunological composition of the tumors, but not their independent effect on long term immune responses initiated in CRT-treated subjects. Our goal is to generate preliminary data addressing whether the addition of pembrolizumab to CRT promotes the modulation of cellular subsets that are likely to be involved in controlling tumor outgrowth and whether concomitant treatment alters patterns of adaptive resistance (checkpoint molecules; immunosuppressive cellular populations; inhibitory cytokines) compared to CRT alone. With respect to immunological outcomes, our expectation is that the addition of pembrolizumab will augment the magnitude and the function of intratumoral and systemic tumor-specific CD8+ T cells (as judged by HPV reactivity), and will lead to increased expression of HLA, MICA and PDL1 compared to CRT alone. We will learn whether pembrolizumab can modulate NK and Treg frequencies in tumors in addition to peripheral blood. Furthermore, we anticipate that CRT will initially deplete tumor infiltrating lymphocytes, but that the consolidation regimen of pembrolizumab post CRT will increase the acuteness and magnitude of the response driven by CRT.

**Systemic response**: Flow cytometry will be used to examine blood for an increase in HLA-DR (a marker of recent T cell activation) expressing CD8+ T cells. ELIspot assays, using overlapping peptide libraries constructed for HPV E2, E5, E6 and E7, will be used to determine whether treatment induces/increases CD8+ T cell responses to defined cervical cancer antigens.

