Human Papillomavirus (HPV) and tumor immunogenicity: DNA is detected in virtually all cervical cancers, and HPV specific CD4+ and CD8+ T cells are found in cervical tumors.[3] The failure of the immune system to eradicate HPV DNA integration is due to cancer cells' acquisition of resistance to cytotoxic T cells, including down-regulation of HLA class I, down-regulation of MHC class I chainrelated molecule A (MICA), production of immune-suppressive cytokines, and induction of FoxP3+ immunosuppressive regulatory T cells.[4] The presence of CD8+ T cells specific for HPV-antigens in cervical cancer subjects is limited, considering the potential immunogenicity of these antigens. Tumor infiltration by lymphocytes could be limited by antigen availability and weak T cell activation; deficiencies in lymphocyte trafficking into tumor; or poor survival and proliferation in the tumor site. In preclinical models, both cisplatin and irradiation have profound influences on the cellular and cytokine components of the tumor; they can lead to the death of immunosuppressive cell subsets, the release of damage associated molecular patterns that can activate DC resulting in increased T cell activation and presence of lymphocytes within tumors. Whether this occurs in human disease has not been assessed. However, irradiation can induce many negative feedback mechanisms, and has the capacity to induce PD-L1 expression either directly, or as a part of adaptive resistance to the effector activity of infiltrating lymphocytes. Furthermore, it is unknown whether low-dose cisplatin will eradicate both regulatory and effector T cells in the tumor site, and whether any HPV-specific CD8+ T cell response can be elicited subsequent to SOC treatment and whether these cells express PD-1 and other inhibitory molecules.

Protocol/Amendment No.: UVA-LACC-PD201, Version 4.0, 06 March 2018

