## 6.0 TRIAL FLOW CHART

## 6.1 Study Flow Chart

# 6.1.1 Arm 1

Trial Period:	Pre- Study	Treatment		Post-treatment		Survival
Visit:	Screening	CRT	Pembro	EOT visit 	Imaging	Follow-
Scheduling Interval:	-42d-1d	W1-W8	W9-W15	35 ± 5d	12w ± 10d post-CRT	Up 
Administrative Procedures						
Informed Consent/ IE	Х					
Demographics/Medical History	Х					
Concomitant Medication Review	Х					
Disease Status						Х
Survival Status						Х
Study Treatments						
Cisplatin		Х				
Radiation		Х				
MK-3475 administration			x 			
Specimen Collection						
Tissue Collection 	Х	x 			Х	
Research Blood Collection	Х	X 			Х	
Clinical Procedures/ Laboratory Assessments						
Pregnancy Test (Urine or Serum) 	х					
Review Adverse Events	Х	Х	Х	Х		

<sup>1 All subjects should be followed for 5 years following treatment to monitor disease status and overall survival. There are no per protocol assessments, all subjects should be monitored according to the standard of care of the treating physicians.

<sup>2 Each subject should return to the clinic for a visit 30-40 days following the last study treatment (of either pembrolizumab or chemoradiation) for assessment of adverse events

<sup>3 Pembrolizumab treatment should be scheduled for every 21 days ( $\pm$  3 days) starting on Week 9.

<sup>4 Fresh tissue biopsies are required. If archival tissue is available these may also be submitted to supplement fresh tissue collected at baseline.

<sup>5 Tissue and blood specimen collected during CRT interval should be obtained at  $5 \pm 2$  weeks

<sup>6 Women of childbearing potential must have a negative pregnancy test within 72 hours of first dose of study treatment.

Trial Period:	Pre- Study	Treat	tment	Post-tre	Survival		
Visit:	Screening	CRT	Pembro	EOT visit 	Imaging	Follow-	
Scheduling Interval:	-42d-1d	W1-W8	W9-W15	35 ± 5d	12w ± 10d post-CRT	Up 	
Physical Examination/ECOG	X7	X 	X 	х	X 		
Vital Signs	Х	Х	Х	Х			
PT/INR and aPTT 	Х						
CBC with Differential 	Х	x 	X 	Х			
Serum Chemistry Panel 	Х	X 	X 	Х			
Thyroid panel 	Х		X 	Х			
	Tumor Imaging/Disease Assessments						

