#### 6.3.4.2.1 Tumor Samples

Tumor tissue samples must be collected at the intervals specified in the Trial Flow Chart, adhering to the following guidelines:

- 1. Pre-study Tissue sample: Fresh tissue must be collected from an office biopsy performed within the 4 weeks prior to start of treatment. If this biopsy yields insufficient tumor tissue, an archival sample may be requested.
- 2. CRT Treatment Sample: Fresh tissue must be collected during CRT treatment, at 5 ± 2 weeks. It is recommended that this sample be obtained at the time of brachytherapy delivery, so that biopsy can be performed conveniently.

Protocol/Amendment No.: UVA-LACC-PD201, Version 4.0, 06 March 2018

3. Treatment completion: Fresh tissue must be collected from an office biopsy performed at 12 weeks ± 10 days following completion of CRT.

Fresh tumor tissue should be divided into portions for several preparations including formalin fixed paraffin embedded (FFPE) in blocks, flash freezing and single cell isolations. Detail instructions for tissue processing and shipping will be provided in a separate study manual.

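### Section 7.2 calls each within-arm pre/post CD8+/Treg comparison a test of pembrolizumab, but it measures chemoradiation plus pembrolizumab, and in Arm 1 the comparison to the end of chemoradiation contains no pembrolizumab

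*Combined protocol and SAP*

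**What the plan says.** Section 7.2 bases the sample size on detecting an effect size of 0.45 "between CD8+/Tregs at baseline and end of CRT, and baseline to the 12 weeks post CRT assessment". It requires 44 eligible patients per arm with type I and II errors of 10%. It then says every within-arm comparison supports one hypothesis: CRT acts on the T cells, and pembrolizumab given with it or afterwards may raise the ratio. The gloss is "test that pembrolizumab will increase CD8+/Tregs to an ES of 0.45".

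The same paragraph expects CRT to act on both parts of the ratio: "Cisplatin can kill T cells, therefore the CRT may eliminate both CD8+ HPV CTL and Tregs". Elsewhere the direction is left open:

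- Section 4.3.1: "irradiation and chemotherapy can recruit myeloid cells and regulatory cells with immunosuppressive function".
- Section 4.3.2.1, on cisplatin and irradiation in preclinical models: "they can lead to the death of immunosuppressive cell subsets".
- Section 4.3.2.1, on the tumour: "we anticipate that CRT will initially deplete tumor infiltrating lymphocytes".

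On timing, the Arm 1 flow chart (6.1.1) places CRT in W1-W8 and pembrolizumab in W9-W15, "starting on Week 9". Section 6.3.4.2.1 says "Fresh tissue must be collected during CRT treatment, at 5 ± 2 weeks", and the last biopsy comes 12 weeks after CRT. Section 7.1.2 lists the pre-to-during-CRT change among the endpoints. Section 7.5 says between-arm differences in pre/post change will be estimated.

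**The concern.** A pre/post change in a single arm combines CRT, pembrolizumab and time. It can be read as a pembrolizumab effect only if CRT leaves the ratio alone, and the protocol expects the opposite. A rise produced by CRT could therefore be reported as a pembrolizumab effect, and a fall produced by CRT could hide a real gain. In Arm 1 the interval to the end of CRT cannot test pembrolizumab at all.

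The trial does collect a randomised comparison that separates the two. At the on-CRT sample, Arm 2 has had CRT with pembrolizumab and Arm 1 has had CRT alone. Section 4.3.2.1 states comparison with CRT alone as a goal, but no section identifies this contrast as the one that answers it. Section 7.5 gives only a t-test power basis for between-arm comparisons and names no adjusted estimator, although 7.3 blocks the randomisation within site.

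**Working it through.** **Inputs.** From 7.2: effect size 0.45, type I and II errors 10%, 44 per arm. From 7.5: between-arm power of 67%, 75% and 87% at effect sizes 0.45, 0.5 and 0.6. From 6.1 and 6.3.4.2.1: the treatment and sampling weeks. Assumed, because the documents do not give them: the CRT-only shift, the pre/post correlation r, and the number of sites.

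**1. The plan's own figure.** Take a paired t-test on within-patient change, two-sided 10%, with d_z the mean change divided by the SD of change. The noncentrality is d_z × √n. At d_z = 0.45 and n = 44 this is 0.45 × √44 = 2.985, against a critical value of t(0.95, 43) = 1.681. Power is 90.2%; n = 43 gives 89.6%. So 44 reproduces, read as two-sided 10%. A one-sided 10% test would need only 34.

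**2. What each comparison contains.** Two arms and two intervals give four comparisons.

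| Comparison | Arm 1 | Arm 2 |
|---|---|---|
| Baseline to end of CRT | CRT only | CRT + pembrolizumab |
| Baseline to 12 weeks post CRT | CRT, then pembrolizumab | CRT + pembrolizumab |

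The flow chart has no collection labelled end of CRT. Whether the term means the 5 ± 2 week sample (Week 7 at the latest) or the literal end of CRT (W8), it precedes the first Arm 1 dose in Week 9.

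**3. Size of the possible misreading.** Same test, n = 44. The middle column assumes no pembrolizumab effect and a CRT rise of the size shown. The last column assumes a true pembrolizumab gain of 0.45 and a CRT fall of the size shown, so the net d_z is 0.45 minus that size; it counts significant increases only.

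| Assumed CRT shift (d_z) | CRT rise, no pembrolizumab effect: test rejects | CRT fall, pembrolizumab +0.45: increase shown |
|---|---|---|
| 0.1 | 17% | 74% (net 0.35) |
| 0.2 | 37% | 49% (net 0.25) |
| 0.3 | 62% | 25% (net 0.15) |
| 0.45 | 90% | 5% (net 0) |

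The reference values are 10% for the middle column and 90% for the last. Counting increases only, the middle column's first entry becomes 16% against a reference of 5%; the others are unchanged after rounding.

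**4. The randomised on-CRT contrast.** A two-sample t-test with 44 per arm, two-sided 10%, gives 67.3%, 75.2% and 87.4% at 0.45, 0.5 and 0.6, which reproduces 7.5. The 90% CI half-width is t(0.95, 86) × √(2/44) = 1.663 × 0.213 = 0.35 SD of change.

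**5. Adjusting for baseline.** With equal pre and post variances, the variance of the ANCOVA estimate relative to the change score is (1 − r²) / [2(1 − r)] = (1 + r)/2. The CI width ratio is its square root.

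| r | CI narrower by | Power at 0.45, SD-of-change units (change score → ANCOVA) | Power at 0.45, raw-SD units (change score → ANCOVA) |
|---|---|---|---|
| 0.3 | 19% | 67% → 83% | 55% → 71% |
| 0.5 | 13% | 67% → 78% | 67% → 78% |
| 0.7 | 8% | 67% → 73% | 86% → 90% |

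Spending up to 9 degrees of freedom on site lowers these powers by less than 0.1 percentage point.

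**The case against.** The strongest reply is that one parenthesis in a sample-size paragraph is being read against the rest of the plan. Section 7.0 seeks preliminary estimates and disclaims definitive comparisons between arms. Section 7.5 describes the powered quantity as change in immune measures, without attributing it to pembrolizumab. Section 4.3.2.1 concedes that the design cannot show the drugs' independent effect on long-term immune responses. The hypothesis in 7.2 itself recognises that CRT acts first. The pre-to-during change and the between-arm estimates are already planned, so what is missing is a pointer. All of this is true, and it makes the problem one of interpretation. It does not correct 7.2, which attaches error rates and the word test to a pembrolizumab effect on the primary immunologic endpoint, including an interval with no pembrolizumab in it. The Arm 1 during-to-post change in 7.1.2 does bracket pembrolizumab, but 7.2 does not size it and it is mixed with recovery from CRT.

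Several points about the numbers also stand:

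- The CRT shifts are illustrative. Rejecting is the correct result for a null of no change under the regimen; the error lies in the attribution.
- Section 7.2 derives 0.45 as Cohen's d_av, whereas the within-arm figures use d_z. If 0.45 is d_av with equal variances, power at n = 44 is about 80%, 90% or 98% at r = 0.3, 0.5 or 0.7, so the 90% starting point is conditional.
- The ANCOVA gain depends on equal variances. With a post-treatment SD half the baseline SD the narrowing is about 50% to 52%; at 1.5 times baseline it is 0% to 7%.
- ANCOVA does not cure the mislabelling. It is an efficiency gain on the contrast that does address the question.

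**Conclusion.** The concern holds. None of the four within-arm comparisons isolates pembrolizumab, and in Arm 1 the one to the end of CRT measures CRT only. This follows from the treatment schedule and needs no assumption about effect sizes. How far a reader could be misled depends on a CRT-only shift whose size and direction are unknown. Over the assumed range of 0.1 to 0.45 SD of change, false attribution runs from 17% to 90%, and the chance of showing a true gain of 0.45 falls to between 74% and 5%. The sample size of 44 per arm is unaffected. This should be corrected, because it decides what the primary immunologic result can be said to show.

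**What to change.** 1. **Section 7.2.** Remove the statement that the within-arm comparisons test pembrolizumab. Suggested text: *Each within-arm test assesses change in CD8+/Treg after CRT plus pembrolizumab; in Arm 1 the on-CRT sample assesses change after CRT only.*
2. **Section 7.5, the contrast.** Name the Arm 2 minus Arm 1 difference at the 5 ± 2 week sample as the estimate of adding concurrent pembrolizumab to CRT. Report it with its 90% CI and the number sampled per arm, since 7.1.2 limits analysis to patients with the required samples. Present it as an estimate, not a powered test. State that it reflects early, partial dosing: with Arm 2 doses nominally on days 1, 22 and 43 and sampling in weeks 3-7, one to three of the three doses have been given. State also that it says nothing about the sequential schedule.
3. **Section 7.5, the estimator.** Estimate between-arm immune contrasts by ANCOVA on the baseline value, with site included as the randomisation stratum.

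The cost is wording in two sections, with no new patients or samples and no change to the sample size. The plan gives up the claim that its primary within-arm test isolates pembrolizumab, and the sequential schedule's own contribution remains descriptive.
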